 - f. History of congenital long QT syndrome or congenital short QT syndrome
 - g. Uncontrolled hypertension (per the Investigator's discretion)

- h. Class III or IV cardiovascular disease according to the New York Heart Association's Functional Criteria
- i. Myocardial infarction within 6 months prior to first study drug administration
- 6. Known history of human immunodeficiency virus or active infection with hepatitis B virus or hepatitis C virus.
- 7. Known uncontrolled intercurrent illnesses, including uncontrolled viral influenza and COVID-19, systemic bacterial infections, and fungal infections.
- 8. Psychiatric disorder or altered mental status that would preclude understanding of the informed consent process and/or completion of the necessary studies.
- 9. Known allergic reactions to H1/H2 antagonists.

Test product, dose and mode of administration:

NBF-006 (10 mg of active ingredient per vial) will be reconstituted with 5.6 mL of the 60 mM sodium acetate diluent (provided by Sponsor) and then diluted with normal saline to 300 mL (or to 320 mL for the 1.6 mg/kg dose level) and administered to the patient via IV infusion.

The infusion will be implemented as a stepwise infusion:

- (1) 0.5 mL/min for 10 minutes,
- (2) then 1.5 mL/min for 10 minutes, and
- (3) finally 6 mL/min for the remaining volume

Total infusion duration of approximately 70 minutes (\pm 20 minutes).

Doses ranging from 0.15 to 1.6 mg/kg will be evaluated. The drug will be administered weekly for 4 weeks, followed by a 2-week rest period. The length of each cycle is 6 weeks.

For detailed instructions on vial concentration, preparation and dispensing, please refer to the Pharmacy Manual.

In the case of an infusion reaction, the infusion should be temporarily interrupted. If symptoms resolve, then resume and complete the stepwise infusion as outlined above. If the symptoms have not resolved by 15 minutes, wait until the symptoms have resolved before resuming the infusion or the patient should receive symptomatic treatment. Recommencing the infusion should only be attempted after reactions have resolved completely. If the infusion reaction does not resolve within one hour after administration of symptomatic treatment (e.g., acetaminophen and/or antihistamines) the dosing should not be resumed the same day. Rechallenge should be discussed with the Medical Monitor, and premedication must be given if the patient receives any further doses.

Dose-limiting toxicity:

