5.4 Withdrawal Criteria

Protocol therapy will be discontinued at any time if any of the following situations occur:

1. Progressive disease (PD).
2. The development of toxicity which, in the Investigator's judgment, precludes further therapy.
3. Patient refusal.
4. Unacceptable AE(s).
5. Lost to follow-up/noncompliance.
6. Intercurrent illness that prevents further administration of treatment.
7. At the discretion of the Investigator.
8. Pregnancy.
9. Study termination.

Additionally, refer to the safety-related stopping rules in Section [8.1.2.11](#).

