6.0 TREATMENT OF SUBJECTS

6.1 Drug Preparation and Administration

NBF-006 is intended for intravenous (IV) infusion use and exposure to direct sunlight should be avoided. Before use, the drug product vial is reconstituted with 5.6 mL of Acetate Diluent to bring the total constituted volume to approximately 6.7 mL, yielding a drug concentration of approximately 1.5 mg/mL. The constituted suspension is diluted into sterile saline diluent to a total volume of 300 mL (or to a total volume of 320 mL for the 1.6 mg/kg dose level) in the clinic for IV infusion to patients. The admixture solution will achieve a final desired drug concentration within acceptable physiological pH and tonicity for IV administration to patients.

NBF-006 infusion will be implemented as a stepwise infusion:

- (1) 0.5 mL/min for 10 minutes,
- (2) then 1.5 mL/min for 10 minutes, and
- (3) finally 6 mL/min for the remaining volume

Total infusion duration of approximately 70 minutes (\pm 20 minutes).

Doses ranging from 0.15 to 1.6 mg/kg will be evaluated. The drug is administered weekly for 4 weeks followed by a 2-week rest period. The length of each cycle is 6 weeks.

For detailed instructions on vial concentration, preparation, and dispensing, please refer to the Pharmacy Manual.

The target infusion time is 70 minutes, but infusion rate will be adjusted as needed (e.g., due to infusion reaction). Premedication with H1/H2 antagonists should be considered if infusion reactions occur; refer to the management of infusion-related reactions (IRRs) outlined in Section [8.1.2.8](#).

The reconstituted drug (NBF-006 in Acetate Diluent) is stable in the glass vial for 2 hours at ambient conditions. The reconstituted drug solution is further diluted to the appropriate dose concentration with saline into a DEHP-free IV bag; this IV infusion solution is stable for 4 hours at ambient conditions. The drug product (lyophilized form, reconstituted solution, and IV infusion solution) should be kept out of direct sunlight.

Both NBF-006 and the Acetate Diluent will be provided by the Sponsor. Ordering instructions will be provided.

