6.2 Dose Interruptions/Withholding for Infusion Reactions or Other Reasons

Guidelines for management of IRRs, including circumstances for interrupting or

discontinuing dosing, are in Section 8.1.2.8.

Study drug may be withheld from a patient based on the Investigator's decision in the event of intercurrent illness, AEs, administrative reasons, or other reasons. If the patient's condition subsequently improves, or the situation that resulted in withholding study drug rectifies itself, the Investigator may resume dosing on the next practical dosing day.

Do not "make up" for missed or skipped doses i.e. if Week 3 dose is missed, do not administer a dose during the rest period (Week 5 or 6). Patients who miss a dose during Cycle 1 may be replaced per Section 5.4.2. The interruption and/or missed dose(s) should be recorded.

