8.1.2.8 Post-Infusion Observation Period

Observe/monitor for any signs and symptoms of IRRs, such as back pain, fever and/or shaking chills, flushing and/or itching, alterations in heart rate and blood pressure, dyspnea or chest discomfort, skin rashes, or anaphylaxis (e.g., generalized urticaria, angioedema, wheezing, hypotension, tachycardia, etc.).

During Part A of the study, each patient must remain in clinic for a minimum 6-hour safety observation period after each NBF-006 infusion until at least three patients at a specific dose level have been reviewed by the Safety Review Committee.

Reductions in the observation period at a given dose level may be recommended by the Safety Review Committee (consisting of Investigators, Theradex Oncology Medical Monitor, and Sponsor) after at least three patients have received a full cycle of treatment (defined as at least four doses and 2-week drug holiday) at that dose level.

Recommendations by the Safety Review Committee for a reduced observation period will be contingent upon:

- Absence of any significant safety concerns following a complete review of all clinical and laboratory data for all treated subjects at the given dose level and the preceding dose levels,
- Absence of any late-onset (>2 hours post-dose) IRRs or IRR symptoms that continue beyond 2 hours post-dose, and lack of any severe or serious IRRs,
- Review and consideration of cytokine and complement activation data at the given dose prior to making a recommendation to shorten the observation period.

If the Safety Review Committee recommends a reduced observation period, the minimum observation period allowed will be 2 hours following EOI from Cycle 2 onward during Part A of the study. Further reductions in the observation period may be suggested by the safety review committee as additional data has accumulated.

For Part B of the study, each patient must remain in clinic for a 6-hour safety observation period after the first dose, 2 hours after EOI for remaining doses in Cycle 1. The observation period may be further reduced to 30 minutes starting Cycle 2, after Medical Monitor and Investigator safety review. The observation period may be lengthened, if clinically indicated.

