8.1.2.9 Management of Infusion-Related Reactions

The guidelines on dose modification and toxicity management for IRRs are outlined in [Table 5](#). All toxicities are graded according to NCI CTCAE Version 5.0.

Table 5: Dosing Modification and Toxicity Management Guidelines for Infusion-Related Reactions		
Severity Grade	Dose Interruption or Modification	Toxicity Management
Grade 1	The infusion should be temporarily interrupted and then resumed when symptoms are resolved.	
If symptoms have not resolved in 15 minutes:
 
 - Acetaminophen and/or antihistamines may be administered per institutional standard at the discretion of the investigator - Consider premedication prior to subsequent doses. - H1 antagonist (e.g., diphenhydramine, hydroxyzine, or chlorpheniramine) and an H2 antagonist (e.g., famotidine) dosed in accordance with approved labelling or the SOC before the start of investigational treatment administration (if premedication is administered parenterally, it should be given within 30 minutes of SOI; if premedication is given orally, it should be given 60-90 minutes prior to SOI). 
If the infusion reaction does not resolve within one hour after administration of acetaminophen and/or antihistamines the dosing should not be resumed the same day. Rechallenge should be discussed with the Medical Monitor, and premedication must be given if the patient receives any further doses.

Grade 2	The infusion should be temporarily interrupted and then resumed when symptoms are resolved.	
Grade 3/4	Permanently discontinue study drug/study regimen	
For Grade 3 or 4:
 
Manage severe IRRs per institutional standards (e.g., IM epinephrine, followed by IV antihistamines, and IV glucocorticoid)

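### The synopsis applies the Grade 1/2 infusion-reaction steps to every grade and omits the Grade 3/4 stop in Table 5; Sections 6.1 and 6.2 point to the wrong section for the rule

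*Protocol*

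**What the plan says.** **Synopsis, under test product, dose and mode of administration.** The paragraph covers an infusion reaction of unspecified grade. The infusion is interrupted, and then: "If symptoms resolve, then resume and complete the stepwise infusion as outlined above". If symptoms persist at 15 minutes, the site waits for resolution or gives symptomatic treatment, with acetaminophen and antihistamines as the examples. The infusion may restart only after complete resolution. If the reaction persists one hour after symptomatic treatment, there is no more dosing that day, and: "Rechallenge should be discussed with the Medical Monitor, and premedication must be given if the patient receives any further doses". The paragraph refers neither to Table 5 nor to Section 8.1.2.9.

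**Section 8.1.2.9, Table 5.** For Grade 1 and for Grade 2: "The infusion should be temporarily interrupted and then resumed when symptoms are resolved". The accompanying management text has the same 15-minute, one-hour and rechallenge steps as the synopsis. For Grade 3/4: "Permanently discontinue study drug/study regimen", with emergency management that includes epinephrine and IV glucocorticoid.

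**Cross-references.** Section 6.1 tells the reader to "refer to the management of infusion-related reactions (IRRs) outlined in Section" 8.1.2.8. Section 6.2 says that the guidelines on interrupting or "discontinuing dosing, are in Section 8.1.2.8". Section 8.1.2.8 is the post-infusion observation period. It opens "Observe/monitor for any signs and symptoms of IRRs" and goes on to set how long patients stay in clinic.

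**The concern.** The synopsis is not a shortened pointer to the rule. It is a complete set of instructions with time limits, and it lacks the one branch that ends treatment. For a Grade 3/4 reaction it and Table 5 give opposite instructions, and nothing in the protocol says which prevails.

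A site working from the synopsis could therefore re-expose a patient after a severe infusion reaction that the protocol's own rule says must end treatment. Someone who starts from Section 6.1 or 6.2 and follows the reference reaches a section without the rule. The protocol itself (Section 2.6) names allergic reaction, complement activation and cytokine release as possible risks of this type of product, and the top dose of 1.6 mg/kg is above any dose reported so far.

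**Working it through.** The point turns on the text. There is no figure in the plan to reproduce.

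**1. The two procedures side by side**

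| Step | Synopsis (no grade stated) | Table 5, Grades 1 and 2 | Table 5, Grade 3/4 |
|---|---|---|---|
| At onset | Interrupt | Interrupt | Stop permanently |
| Symptoms resolve | Resume and complete | Resume | No resumption |
| Unresolved at 15 min | Wait or treat symptoms | Acetaminophen and/or antihistamines may be given | Manage as a severe reaction |
| Unresolved 1 h after treatment | No more dosing that day | No more dosing that day | Already stopped |
| Later doses | Discuss rechallenge; premedication required | Same sentence as the synopsis | None |

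The synopsis column matches the Grade 1/2 column step by step, down to an identical rechallenge sentence. It departs from the Grade 3/4 column at every step.

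**2. What follows for a Grade 3/4 reaction**

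- It clears completely, at the latest within one hour of symptomatic treatment: the synopsis leads to same-day resumption, Table 5 to permanent discontinuation.
- It does not clear in that time: the synopsis leaves rechallenge on another day open, Table 5 does not.

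**3. Does another passage supply the stop?**

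- Section 5.4 ends therapy for toxicity that the investigator judges to preclude treatment, or for unacceptable adverse events. Both need judgment and neither names a grade.
- Section 4.5 and the matching synopsis text end treatment at intolerable toxicity, again a matter of judgment.
- The DLT lists (synopsis and Section 6.1.3) count a Grade 3 or higher infusion-related reaction as a DLT. That governs cohort decisions in Part A and does not tell the site to stop the drug in that patient.
- Section 8.1.2.11 covers Grade 5 toxicity only.
- Section 6.3 discusses premedication after infusion-related reactions without a grade.

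Table 5 is the only place where the Grade 3/4 stop is stated.

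**4. The references to Section 8.1.2.8**

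There are five. Three concern the observation period and are correct: the notes to Tables 3 and 4, and Section 7.3. Two concern management of the reaction and are wrong: Sections 6.1 and 6.2. The rule they mean is in 8.1.2.9.

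**5. Scale, for context only**

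Infused volume at 1.6 mg/kg (320 mL), from the stepwise rates in Section 6.1:

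- By minute 20: 0.5 × 10 + 1.5 × 10 = 5 + 15 = 20 mL given. Remaining: 300/320 = 94%.
- By minute 45: 20 + 25 × 6 = 170 mL given. Remaining: 150/320 = 47%.
- Full duration: 20 + 300/6 = 70 minutes, which agrees with the stated infusion time.

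The onset times of 20 and 45 minutes are illustrative assumptions. The volumes would be the same after a Grade 1 reaction, so they show only how much drug resuming and completing would deliver.

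Section 2.4 reports no treatment-related Grade 3–4 adverse event in 14 patients at levels 1–4. The one-sided 95% upper limit for 0/14 is 1 − 0.05^(1/14) = 0.193, or 19%. It covers all related Grade 3–4 events, not infusion reactions alone, and comes from patients treated at 1.2 mg/kg or below. The clean record so far therefore does not rule out severe reactions, but it does not measure their rate at 1.6 mg/kg.

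**The case against.** The strongest reply is that the rule is settled and easy to find. Table 5 is explicit, its title appears in the list of tables, and a reader sent to 8.1.2.8 meets 8.1.2.9 as the next heading. A synopsis summarises. Its examples of treatment suit mild reactions, whereas epinephrine appears only in the Grade 3/4 row, so a clinician would read the paragraph as describing mild reactions and would be unlikely to resume after a severe one. The synopsis also lists a severe infusion reaction as a DLT and says that intolerable toxicity ends treatment. Rechallenge must be discussed with the Medical Monitor, which acts as a check. The volume figures and the 0/14 limit do not measure how often the conflict would arise.

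Much of this stands as a limit on weight. The rule is decided, the pointers miss by one adjacent subsection, the frequency is unknown, and the figures are only context. None of it removes the conflict. The synopsis trigger is any infusion reaction, and its time-limited steps are directive. Intolerable and unacceptable toxicity are matters of judgment where Table 5 leaves none. A DLT label does not stop the drug in that patient. The discussion with the Medical Monitor applies only to rechallenge; same-day resumption has no such check.

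**Conclusion.** The concern holds. For Grade 3/4 infusion reactions the synopsis gives the wrong action: it allows resumption on the same day if the reaction clears in time, and leaves rechallenge open if it does not, where Table 5 requires permanent discontinuation. For Grades 1 and 2 the two texts agree. Two of the five references to Section 8.1.2.8 are wrong, and they are the two that should lead to the stopping rule.

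This should be fixed because a stated dosing instruction contradicts the protocol's own safety rule. It is a wording fault rather than an open design question, and no endpoint, DLT definition, escalation rule or analysis is affected. The conclusion rests on reading the synopsis as written and on the absence of any statement that the body overrides it. It does not depend on an assumed frequency of severe reactions, which the documents do not give.

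**What to change.** 1. In the synopsis, limit the infusion-reaction paragraph to Grade 1 and Grade 2 reactions.
2. Add a sentence there: for a Grade 3 or 4 reaction, study drug is permanently discontinued (see Table 5, Section 8.1.2.9).
3. In Sections 6.1 and 6.2, change the reference from 8.1.2.8 to 8.1.2.9. Leave the other three references to 8.1.2.8 as they are.

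The cost is one limiting phrase, one sentence and two section numbers. No new rule is created; the synopsis is brought into line with the rule already in Table 5.

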1.0 GENERAL INFORMATION

1.1 Protocol Number and Title of the Study

Protocol No. NBF-006-001, "A Phase I/Ib Open-Label, Multi-Center, Dose-Escalation Study to Investigate the Safety, Pharmacokinetics and Preliminary Efficacy of Intravenous NBF-006 in Patients with Non-Small Cell Lung, Pancreatic, or Colorectal Cancer Followed by a Dose Expansion Study in Patients with KRAS-Mutated Non-Small Cell Lung Cancer"

1.4 Signature Authorization

Theradex Oncology will act as the Sponsor Representative.

2.0 BACKGROUND INFORMATION

2.1 Introduction

Mutations of genes encoding protein kinases in the mitogen-activated protein kinase (MAPK) (KRAS/RAF/MEK/ERK) and phosphatidylinositol-3-kinase (PI3K) (PI3K/Akt/mTOR) signal-transduction pathways can alter the normal cellular kinase cascade regulatory function, resulting in the dysregulation of cellular proliferation, apoptosis, survival and cell migration common to tumor cell development and tumor progression ([Figure 1](#)). In the MAPK pathway, oncogenic Kirsten rat sarcoma (KRAS) drives the activation of the subsequent signaling proteins (RAF/MEK/ERK) and is known to be mutated frequently in pancreatic, colorectal, lung and gastric adenocarcinomas, as well as multiple myeloma and endometrioid carcinoma.¹ The PI3K pathway is regulated by the phosphatase and tensin homolog (PTEN) tumor suppressor and activated by guanosine triphosphate-RAS (GTP-RAS). Mutations of PTEN and KRAS thus alter the control of this important signaling pathway and multiple effector components of the PI3K pathway are known to be frequently mutated or altered in

a large variety of cancers.^{2,3}

[figure not shown]

Figure 1: Interactions Among Several Key Components Involved in the MAPK and PI3K Pathways

KRAS is a member of the GTPase family of proteins, which switches to active mode when bound to GTP and inactive mode when bound to guanosine diphosphate. In pathological condition, KRAS mutation results in KRAS-GTP driving oncogenesis. Activation of KRAS phosphorylates and activates downstream targets, such as MEK/ERK in the MAPK pathway and Akt/mTOR in the PI3K pathway. This activation results in increased growth and proliferation.

With the central role of these two signaling pathways in cancer, the inhibition of KRAS and the signaling pathway effector proteins has been a major focus of cancer pharmaceutical research. The mutated KRAS oncoprotein itself has been difficult to target for inhibition due to difficulties in overcoming the impaired GTP hydrolysis of mutant KRAS, similarities of mutant and wild-type KRAS, and the availability of alternate mechanisms for required KRAS membrane association in the face of farnesyl transferase inhibition.^{1,4} As a result, while KRAS inhibition remains an ongoing research undertaking, therapies inhibiting specific downstream effector signaling proteins along both pathways comprise the majority of targeted agents currently available or in development.

Nitto BioPharma, Inc. has targeted glutathione S-transferase pi (GSTP), one of a multigene

family of glutathione S-transferases (GST) isoenzymes that exist as mitochondrial, microsomal, or cytosolic enzymes involved in catalyzing thioether bonds between glutathione and electrophilic toxins and protecting cells from cellular oxidative stress.⁵ Importantly, GSTP is also a significant protein in cancer cells and is implicated in the modulation of multiple signaling proteins in the RAS and PI3K pathways. GSTP has been detected at high levels in many tumors including ovarian, non-small cell lung, breast, colon, pancreas and lymphomas and has been associated with cancer disease progression as well as chemotherapy drug resistance.^{5,6} GSTs have been recognized for their ability to bind structurally to diverse non-substrate ligands. In this non-enzymatic role, GSTs function to sequester the kinase in a complex, thus preventing it from acting on downstream targets.

GSTs are involved in detoxification of many potentially carcinogenic compounds. The homozygous deletions or null genotypes of GSTT1 (theta class) can be found in varying frequency in the normal population and may be associated with cancer incidence and drug effects. The frequency of GSTT1-null varies widely in different populations: approximately 50-60% in Asians, 15% in White populations, 15-20% in Blacks or African Americans, and less than 10% in Hispanic populations.⁷

GSTP has been implicated in regulation of cell signaling in response to intra- and extracellular stimuli in many pathways involving MAPKs. The result of this action is a regulation of pathways that control cell proliferation and apoptotic cell death. For example, GSTP was among the first isoenzymes found to inhibit c-JUN N-terminal kinase (JNK) through direct protein-protein interaction. JNK is a MAP kinase involved in stress response, apoptosis, inflammation, and cellular differentiation and proliferation. Thus, elevated expression of GSTP also has an anti-apoptotic role in tumor cells by interacting directly with MAPK/JNK through binding of the C-terminus of JNK.⁸

2.2 The Investigational Product

The drug product, NBF-006 contains a novel active pharmaceutical ingredient (API), NDT-05-1040, a small interfering ribonucleic acid (siRNA) encapsulated within lipid nanoparticles (LNPs). The LNP is composed of 5 key lipids, designed to inhibit the expression of GSTP messenger ribonucleic acid (mRNA) and protein in tumors and lung tissue. Before use, NBF-006 is reconstituted with 60 mM Sodium Acetate Diluent (Acetate Diluent), which will also be provided by the sponsor.

The significant technological achievement of this program is to provide effective extrahepatic delivery of siRNA. Historically, LNPs have tended to deliver cargo exclusively to the liver. NBF-006 was designed to distribute the siRNA cargo primarily to tumors and the lung. The current preclinical development of NBF-006 has been focused on KRAS-mutant non-small cell lung cancer (NSCLC) given the unmet medical need and the ability to deliver siRNA to lung tumors in preclinical models.

Importantly, NBF-006 delivery is also achieved in other organ locations and the pleiotropic effects of GSTP on the key pathways of many cancers indicate that the siRNA knockdown (KD) of GSTP protein expression may be effective for other cancer indications. Once the safety profile and preliminary anti-cancer activity of NBF-006 is established with this Phase I/Ib clinical trial, the efficacy of NBF-006 in additional malignancies may be explored.

